At any time during the treatment period, subjects will be withdrawn from further dosing if they develop any of the following features on MRI: vasogenic edema, macrohemorrhage, an area of superficial siderosis or a symptomatic microhemorrhage. If discontinued from study drug, subjects will undergo an Early Termination Visit (within 7 days after discontinuation) and will attend the Follow-Up Visit (3 months after this decision). They will also undertake an unscheduled visit (with MRI) at approximately 30 days after the visit at which such MRI features were first identified. MRI will also be performed at approximately the time of the Follow-Up Visit. Additional visits for safety may be arranged if clinically indicated in the opinion of the investigator, including after 90 days since the final dose of study drug. In addition, subjects who discontinue from study drug are expected to return after the Early Termination Visit for each scheduled visit when the clinical efficacy assessments are to be conducted per the Schedule of Procedures/Assessments. At these visits, safety information (in addition to efficacy assessments) on concomitant medications, AEs, and SAEs will be collected. (revised per Amendment 01)

At any time during the Treatment Period, subjects who have nonsymptomatic, treatment-emergent microhemorrhages found on MRI, but none of the features which merit discontinuation of treatment (ie, vasogenic edema, macrohemorrhage, an area of superficial siderosis, or a symptomatic treatment-emergent microhemorrhage) may continue with treatment. These subjects will have safety assessments (including MRI) at approximately 30 days after the visit at which such MRI features were found. They will also continue with the scheduled MRI scans. The safety MRI must be reviewed by both the imaging vendor and a local reader prior to administration of the next dose of study drug for each respective visit. (revised per Amendment 06) Additional unscheduled MRI scans may be arranged on an individual subject basis in discussion with the study medical monitor.

An assessment of suicidality using the C-SSRS will be performed at Screening and Baseline and at designated time points.

Extension Phase Part A (revised per Amendments 08, 11, 16, and 17)

During the Extension Phase, safety assessments will be performed according to the Schedule of Assessments and all AEs and SAEs recorded.

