At the time of Amendment 11, the Core Study was completed. Preliminary data analysis indicated that the incidence of amyloid-related imaging abnormality edema/effusion (ARIA-E) was less than 10% for the highest BAN2401 dose groups (10 mg/kg biweekly and monthly) and less than 8% overall for subjects receiving treatment with any dose level of BAN2401. There were 5 cases of symptomatic ARIA-E in BAN2401 treatment groups (all developed ARIA-E within the first 12 weeks of treatment): 1 severe ARIA-E on magnetic resonance imaging (MRI) at 2.5 mg/kg biweekly, reported as a non-serious AE; 1 mild ARIA-E on MRI at 10 mg/kg monthly, reported as a serious adverse event (SAE); 1 moderate ARIA-E on MRI at 10 mg/kg biweekly, reported as an SAE; and 2 severe ARIA-E on MRI at 10 mg/kg biweekly, both reported as SAEs. The breakdown of ARIA-E cases by ApoE4 status is provided in [Table 2](#), with the incidence being higher in ApoE4 carriers (<15% at top dose) than non-carriers (8% at top dose). (revised per Amendment 11)

Table 2 Summary of Treatment-Emergent ARIA-E by ApoE4 Status (Safety Analysis Set) (revised per Amendment 11)

Category	Placebo (N=245) n (%)	BAN2401							
		2.5 mg/kg biweekly (N=52) n (%)	5 mg/kg monthly (N=51) n (%)	5 mg/kg biweekly (N=92) n (%)	10 mg/kg monthly (N=253) n (%)	10 mg/kg biweekly (N=161) n (%)	Total BAN2401 (N=609) n (%)		
		ARIA-E	2 (0.8)	1 (1.9)	1 (2.0)	3 (3.3)	25 (9.9)	16 (9.9)	46 (7.6)
		APOE4 positive	2/174 (1.1)	1/38 (2.6)	1/40 (2.5)	3/84 (3.6)	23 ^a /225 (10.2)	7/49 (14.3)	35/436 (8.0)
APOE4 negative	0/71	0/14	0/11	0/8	2/28 (7.1)	9/112 (8.0)	11/173 (6.4)		

APOE4 = apolipoprotein ε4 variant, ARIA-E = amyloid-related imaging abnormality edema/effusion, TEAE = treatment-emergent adverse event

a: One additional ApoE4 positive ARIA-E case was observed after 18 month treatment database lock and after treatment discontinuation; therefore, by definition was not treatment-emergent and is not counted in this table or TEAE description above

After 18 months of treatment in any BAN2401 dose group overall, there were few reported cases of ARIA-E (n=46/609, 7.6%). Most cases of ARIA-E (approximately 61%) occurred within the first 3 months of treatment, were mild to moderate in radiographic severity on MRI, were asymptomatic (92%), and typically resolved within 4 to 12 weeks. (revised per Amendment 11)

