Appendix 4 EXTENSION PHASE PART A (revised per Amendments 11, 16, 17, 18, and 19)

PRIMARY OBJECTIVE

To evaluate the long-term safety and tolerability of BAN2401 in subjects with EAD

SECONDARY OBJECTIVE

To assess if the treatment benefit in brain amyloid levels (as measured by amyloid PET) at the end of the Core Study will be maintained over time in the Extension Phase Part A in subjects with EAD

EXPLORATORY OBJECTIVES

1. To evaluate the clinical effects of BAN2401 in subjects with EAD on the ADCOMS, CDR-SB, ADAS-Cog, and MMSE over time during the Extension Phase Part A
2. To assess time to disease progression as evaluated CDR global score during the Extension Phase Part A (revised per Amendment 12)
3. To explore the long-term effects of BAN2401 in subjects with EAD on total hippocampal volume and other biomarkers (eg, plasma biomarkers) annually in the Extension Phase Part A (revised per Amendment 15)
4. To characterize population PK of BAN2401 in subjects enrolled in the Extension Phase Part A of the study
5. To evaluate patterns of resource utilization and associated costs of care for subjects with EAD and their study partners, using medical claims data (revised per Amendment 16)

Objectives for the Dosing Regimen Substudy (revised per Amendment 17)

1. To assess whether amyloid levels are maintained over time at less frequent dosing regimens as measured by positron emission tomography standard uptake value ratio (PET SUVR)
2. To assess the effect of less frequent dosing regimens on the changes in plasma biomarkers
3. To explore the clinical effects of less frequent dosing regimens in subjects with EAD on ADCOMS, CDR-SB, ADAS-Cog, and MMSE over time
4. To evaluate the long-term safety and tolerability of BAN2401 in subjects with EAD at less frequent dosing regimens
5. To characterize population PK and PK/PD (biomarker and PET SUVR [when available]) of BAN2401 in subjects enrolled in the Dosing Regimen substudy of the study

ELIGIBILITY CRITERIA (revised per Amendment 12)

Inclusion:

1. Subjects who have completed Visit 42 (Week 79) of the Core Study or who discontinued study drug during the Core Study due to any of the following reasons:
 - a. ARIA-E
 - b. amyloid related imaging abnormality hemorrhage (ARIA-H) (superficial siderosis, macrohemorrhage, or symptomatic microhemorrhage)

- c. Prohibited or restricted medications that were prohibited during Core Study conduct but are no longer prohibited in the Extension Phase

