- Are currently abstinent, and do not agree to use a double-barrier method (as described above) or refrain from becoming sexually active during the study period or for 28 days after study drug discontinuation.
- Are who are using hormonal contraceptives but are not on a stable dose of the same hormonal contraceptive product for at least 4 weeks before dosing and who do not agree to use the same contraceptive during the study and for 28 days after study drug discontinuation.

(NOTE: All females will be considered to be of childbearing potential unless they are postmenopausal [amenorrheic for at least 12 consecutive months, in the appropriate age group, and without other known or suspected cause] or have been sterilized surgically [ie, bilateral tubal ligation, total hysterectomy, or bilateral oophorectomy, all with surgery at least 1 month before dosing]).

4. Subjects who develop the following conditions from the time of completion of the Core Study to the start of the Extension Phase:
 - a. Contraindications to MRI scanning, including cardiac pacemaker/defibrillator, ferromagnetic metal implants (eg, in skull and cardiac devices other than those approved as safe for use in MRI scanners)
 - b. Other significant pathological findings on brain MRI at Extension Phase Baseline (Extension Screening Visit), including but not limited to: any macro-hemorrhage (greater than 10 mm at greatest diameter), which is currently symptomatic or worsened since the Core Study; any area of superficial siderosis, which is currently symptomatic or worsened since the Core Study; evidence of vasogenic edema, which is severe or symptomatic; aneurysms, vascular malformations, infective lesions, evidence of multiple lacunar infarcts or stroke involving a major vascular territory, severe small vessel, or white matter disease or space occupying lesions or brain tumors (however lesions diagnosed as meningiomas or arachnoid cysts and <1cm at their greatest diameter need not be exclusionary)
 - c. Any immunological disease which is not adequately controlled, or which requires treatment with biologic drugs during the study
 - d. Bleeding disorder that is not under adequate control (including a platelet count <50,000 or INR >1.5)
 - e. Receiving treatment with anticoagulant therapy but anticoagulation control is not optimized and is stable for at least 4 weeks before Extension Phase Baseline (Extension Screening Visit)

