Those subjects who develop symptomatic or radiographically severe treatment emergent ARIA-E will be temporarily stopped from study drug administration until the ARIA-E resolves radiographically, and will be followed up to resolution of the event (including symptoms, if any). They will undertake an unscheduled safety visit (with MRI) at approximately 30 days and another safety visit (with MRI) at approximately 90 days (which may be unscheduled or scheduled visit) after the symptomatic or severe ARIA-E was first identified. Thereafter, these subjects will have a safety visit (with MRI) at approximately 30 days (which may be an unscheduled or a scheduled visit) until the ARIA-E has resolved both radiologically and clinically. During treatment interruption, time will elapse on the Schedule of Assessments when the scheduled visit would otherwise occur. Once the ARIA-E has resolved both radiologically and clinically, they may then resume treatment for the study duration and study assessments on the Schedule of Assessments. Resumption of treatment following symptomatic ARIA-E can only occur twice, after which the subject must be discontinued from the study. (revised per Amendment 12)

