Appendix 5 EXTENSION PHASE PART B (revised per Amendment 19)

PRIMARY OBJECTIVE:

To evaluate the long-term safety and tolerability of BAN2401 in subjects with EAD

ELIGIBILITY CRITERIA

Must be currently enrolled in Extension Phase Part A.

STUDY DESIGN AND PLAN

All subjects ongoing in Extension Part A upon implementation of Protocol Amendment 19 will transition to Extension Part B. Extension Phase Part A and Part B combined will continue for up to 60 months (5 years), or until BAN2401 is commercially available for individual subjects at each study site, at which time the subjects will switch to commercial BAN2401, or in the cases where drug is not yet commercially available, treatment will continue until the benefit to risk ratio from treatment with BAN2401 is no longer considered favorable, whichever comes first. Upon transition to Extension Phase Part B, Dosing Regimen substudy subjects will be given the option to remain on their current dosing regimen or transition back to BAN2401 10 mg/kg biweekly infusions.

Subjects in Extension Phase Part B will have procedures and assessments including periodic safety assessments at approximately 6 monthly intervals (± 4 weeks) or as unscheduled assessments, when required.

All infusions will take place in the clinic; however, if approved by the Sponsor and allowable and conducted according to country and local guidelines, subjects will be offered the option of home infusions for approved visits. Home infusions are being implemented as a result of the Coronavirus Disease 2019 (COVID-19) pandemic to allow subjects who cannot visit clinical sites for various reasons to continue receiving treatment. Home infusions will be allowed per Sponsor approval according to country and local guidelines during the COVID-19 pandemic and following its resolution, where permitted.

Subjects will continue in Extension Phase B for a maximum combined (Part A and Part B) open-label treatment duration of up to 60 months (5 years), or until BAN2401 is commercially available for individual subjects at each study site, at which time the subjects will switch to commercial BAN2401, or in the cases where drug is not yet commercially available, treatment will continue until the benefit to risk ratio from treatment with BAN2401 is no longer considered favorable, whichever comes first.

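### Outside Japan, the limit of two restarts after ARIA-E counts symptomatic events only, although asymptomatic severe ARIA-E also stops dosing

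*Protocol*

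**What the plan says.** The ARIA-E rule for sites outside Japan has three steps, worded alike in the Synopsis (ARIA Management), Appendix 4 (Extension Part A) and Appendix 5 (Extension Part B).

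- **Hold:** "Those subjects who develop symptomatic or radiographically severe treatment emergent ARIA-E will be temporarily stopped from study drug administration".
- **Restart:** "Once the ARIA-E has resolved both radiologically and clinically, they may then resume treatment for the study duration".
- **Limit:** "Resumption of treatment following symptomatic ARIA-E can only occur twice, after which the subject must be discontinued from the study".

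Appendix 5 is the text that governs future dosing, because "All subjects ongoing in Extension Part A upon implementation of Protocol Amendment 19 will transition to Extension Part B".

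Asymptomatic mild or moderate ARIA-E outside Japan does not stop dosing. The severe grade is defined by extent on FLAIR, above 10 cm in one dimension, without reference to symptoms.

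**The concern.** The events that stop dosing form a wider set than the events that count toward the limit. Asymptomatic severe ARIA-E belongs to the first set and not to the second.

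The result runs against the ordering of severity. A radiographically mild but symptomatic episode counts toward mandatory discontinuation. An episode in the worst radiographic grade does not count if the subject reports no symptoms. As written, a third or later re-challenge at 10 mg/kg after severe ARIA-E is permitted.

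Re-challenge is a deliberate part of this Extension. Appendix 4 admits subjects "who discontinued study drug during the Core Study due to any of the following reasons", and ARIA-E is the first reason listed. The DSMB's remit, according to the Synopsis, ends with the Core Study, so there is no independent board to notice repeated re-challenge in the Extension.

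**Working it through.** No sample-size, power or alpha figure is involved. The check compares, for each ARIA rule in the Extension, what stops dosing with what counts toward the limit.

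| Rule (Synopsis, Appendices 4 and 5) | Stops dosing | Counts toward two restarts | Match? |
|---|---|---|---|
| ARIA-H | Symptomatic | Symptomatic | Yes |
| ARIA-E, Japan | Symptomatic, or radiographically moderate or severe | Symptomatic, and/or moderate or severe | Yes |
| ARIA-E, outside Japan | Symptomatic, or radiographically severe | Symptomatic | **No** |

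The third row is the only one in which a class of event stops dosing and is left without a number.

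**Does another section close the gap?**

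- The safety-related discontinuation lists in Appendices 4 and 5 cover infusion reactions, meningoencephalitis and hypersensitivity with tissue injury. ARIA-E is not on either list.
- Section 9.3.3 stops study drug for vasogenic edema, but expressly in the Core Study.
- The Brain MRI text in Section 9.5.1.5 has a similar withdrawal rule without naming the Core Study. The Synopsis places the matching rule ("subjects will be withdrawn from further dosing if they develop any of the following features on MRI: vasogenic edema") under the Core Study, and Section 9.5 refers Extension assessments to Appendices 4 and 5. Applying it to the Extension would also contradict the permission to restart.
- Section 9.4.8 asks investigator and sponsor to consider continuation after missed infusions. It sets no number.

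**Does the protocol separate the two classes elsewhere?** At Extension entry it does not. Exclusion 4b in Appendix 4 (32b in the Synopsis) bars "evidence of vasogenic edema, which is severe or symptomatic".

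**How often could this arise?** Section 7.1.2.3 gives the Core Study counts.

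- ARIA-E on BAN2401: 46/609 = 7.6%.
- Symptomatic: "There were 5 cases of symptomatic ARIA-E in BAN2401 treatment groups". Of these, 1 (2.5 mg/kg biweekly) + 2 (10 mg/kg biweekly) = 3 were radiographically severe.
- Asymptomatic: 46 − 5 = 41, and 41/46 = 89%. The section states 92%, which would be 0.92 × 46 = 42.3. The difference does not affect this point.
- Severe among the asymptomatic: not stated. The section says most cases were mild to moderate. Taking most to mean more than half, at least 24 of the 46 were mild or moderate and at most 22 were severe. Removing the 3 symptomatic severe cases leaves between 0 and 22 − 3 = 19.
- Recurrence on re-challenge: not available, because Core dosing ended at the first vasogenic edema.

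The range of 0 to 19 concerns first episodes over five dose regimens. The quantity that matters is subjects who reach a third restart in the Extension, and it cannot be derived from these figures.

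**The case against.** The best opposing case is that the narrower limit may be a clinical choice and that each episode is already supervised.

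- **Supervision.** Restart is permitted, not required, and only after radiological and clinical resolution. A safety MRI must be read by the vendor and a local reader before the next dose (Table 13 footnote h, Table 16 footnote m). Part A requires event details to go to the Medical Monitor. Section 9.4.8 adds a joint investigator and sponsor review after missed infusions, and with typical resolution in 4 to 12 weeks a hold on biweekly dosing would trigger it. The investigator may withdraw a subject at any time. All of this stands, and it makes harm less likely. None of it sets a number.
- **Symptom-based scheme.** Asymptomatic ARIA-H, even a macrohemorrhage over 10 mm, does not stop dosing, so tying discontinuation to symptoms could be the general principle. This does not carry over to ARIA-E, where severity alone does stop dosing.
- **Entry criterion.** Barring severe or symptomatic edema at the Extension baseline MRI resembles holding until resolution and says nothing about how many restarts are acceptable. That is fair: it shows the two classes treated alike at entry and no more.
- **Intent.** ARIA management was revised under Amendments 12, 13 (Japan only) and 20, and the global sentence still names symptomatic events only. The Japan text was a separate change and shows that matched wording was available, not what the global rule was meant to say. Intent remains open.
- **Reach.** Three separate, fully resolved, asymptomatic severe episodes in one subject would be unusual, and routine MRI in Part B is about every 6 months. This is accepted.

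**Conclusion.** The point holds. Outside Japan, the Extension limits restarts to two after symptomatic ARIA-E of any grade and states no limit after asymptomatic severe ARIA-E, although both stop dosing and both allow restart. No other section fills the gap.

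The practical reach is probably very small and cannot be quantified from the protocol, since the gap has effect only from the third restart in one subject. It is a gap in a safety rule and touches no statistical result. The conclusion rests on reading the limit literally and on taking the vasogenic edema withdrawal text in Section 9.5.1.5 as applying to the Core Study. It does not assume that the omission was a mistake. It is worth fixing because the correction is cheap and the omitted class is the worst radiographic grade.

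**What to change.** In the Synopsis (ARIA Management), Appendix 4 and Appendix 5, extend the limit so that it applies to restarts after *symptomatic and/or radiographically severe ARIA-E*. This makes the limit match the hold, as the Japan rule already does. Appendix 5 matters most, since it governs dosing once subjects have moved to Part B.

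If the narrower limit is deliberate, say so in those three places and give the clinical reason.

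The cost is one phrase in three places by amendment, and the earlier discontinuation of the few subjects, if any, who have repeated asymptomatic severe ARIA-E.
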